### 2.2. TARGETED THERAPY IN LUNG CANCER

Targeted therapies implemented in standard care are directed at the activated products of mutated epidermal growth factor receptor (EGFR) (5) or ALK translocation (6). Such therapies have shown high response rates, and improved progression-free survival (PFS). However, these monotherapies apply to only small subsets of oncogene-driven patients, and virtually all develop resistance and succumb to their disease (7). Relapse occurs mostly as a consequence of the Darwinian selection of tumor clones harboring genomic variants that lead to the activation of additional signaling pathways and, hence, resistance. This is perhaps not unexpected, as tumors often exhibit a large variety of molecular abnormalities (7, 8), even at diagnosis. Heterogeneity across tumor clones is amplified in metastases, and in response to therapeutic pressure.

### 2.3. LIMITATIONS OF CURRENT TARGETED THERAPY APPROCHES

As mentioned, in NSCLC, as well as in many cancer types, molecular characterization of the tumors has resulted in segmentation of nosological classifications, based previously on the organ of origin and histology, into a variety of molecular subtypes, often characterized by one specific driver molecular genetic alteration (5, 9). However, this strategy has several limitations: (i) only a portion

of tumors have an identified driver mutation, and many of these simple models may have been already described (10, 11); (ii) there is no recognized strategy to efficiently pinpoint unrecognized drivers within the complex and multiple genomic alterations observed in most tumors; (iii) targeted treatments are not uniformly efficient even in these selected subgroups; (iv) the majority of tumors are actually driven by multiple aberrant genes (9, 12, 13), making the monotherapy paradigm unsuitable for most metastatic cancers; and (v) resistance uniformly emerges in a Darwinian manner in patients treated with a single targeted therapy.

## 2.4. COMBINATION THERAPY AND CANCER

Combination of cytotoxic therapies has been demonstrated to be effective where single agents provide only moderate benefits, as illustrated in Hodgkin's lymphoma. Whether this paradigm applies to targeted therapy remains unclear for most diseases. However, recently, combinations targeting the same pathway in BRAF-mutant melanoma (14) (using trametinib (MEK inhibitor) together with dabrafenib (BRAF inhibitor)), or resistance pathways (combining PIK3CA and MEK inhibitors) (15) showed some efficacy, either pre-clinically and/or in the clinic.

With the aim of further enhancing clinical benefit and increasing survival, we intend to explore the efficacy of triple regimen therapy, following the historical success in diseases such as acquired immunodeficiency syndrome. The major challenges for this effort are delineating the scientific rationale for matching agents with patients' tumors, while being cognizant of potential toxicity for multi-drug regimens.

## 2.5. PREVIOUS EXPERIENCE - WINTHER STUDY

The study workflow and the use of dual biopsies were previously investigated in the WINTHER trial (<http://clinicaltrials.gov/show/NCT01856296>) of the Worldwide Innovative Networking (WIN) Consortium ([www.winconsortium.org](http://www.winconsortium.org)) for personalized cancer therapy (PI: [name]; Co-PI: [name]). WINTHER was built as a molecularly driven navigation trial. It was developed on the shoulders of previous trials:

- (i) The biomarker-driven trial pioneered by [name], which was one of the first to show that using biomarkers was feasible, and that, by using patients as their own controls (looking at PFS2 on matched therapy versus prior PFS), improved outcomes could be demonstrated without randomization (16).
- (ii) BATTLE study (17), which proved definitively that molecular profiling on fresh biopsies in lung cancer was feasible and safe.
- (iii) PREDICT, a navigation trial that showed that molecular matching (albeit non-randomized) was associated with substantially increased response rates PFS, OS, and PFS2/PFS1 ratio, even in the Phase I setting (18).
- (iv) NCI-Match, which started in 2015 and uses a similar molecularly driven, non-randomized strategy (19, 20).
- (v) Lung-Map in USA and CR-UK Matrix Lung in UK.

To date, the WINTHER study has been activated in 6 cancer centers (Gustave Roussy, Centre Léon Bérard, Chaim Sheba Medical Center, Val d'Hebron, MD Anderson Cancer Center and McGill Segal Cancer Center) across 5 countries (France, Spain, Israel, Canada, USA). The study has accrued

more than 300 patients (study ongoing). The WINTHER study includes dual biopsies from both normal and tumor tissues and stratifies patients in different arms, i.e. Arm A (genomics, Next Generation Sequencing, Foundation Medicine) and Arm B (transcriptomic data, which uses the dual biopsies to compare the transcript levels in tumor to corresponding normal tissue) has been used to direct matched therapy. Specifically, patients who harbor a targetable genomic alteration are stratified to Arm A; patients with no targetable genomic alteration are stratified to Arm B and the choice of therapy is based on mRNA expression profiling analyzed by an algorithm. In the WINTHER trial, weekly Clinical Monitoring Committees (CMC) were successfully established (with calls occurring each Monday evening and allowing patients presentation, review of -omics data, and therapy suggestions by the participating physicians from the five countries). There have been no serious safety signals to date, and the dual biopsies have proven safe and feasible.

**The following elements have been established for WINTHER and will be used by the SPRING trial:**

- Dual biopsies of tumor and normal matched tissue in solid tumors (including lung) patients. No significant safety issue encountered, with 246 patients having undergone dual biopsies.
- Use of both genomics and transcriptomics in the clinical setting was possible, under stringent quality control.
- Multi-country trial across 6 centers and 5 countries (France, Spain, Israel, Canada and USA) - approved by IRB and regulatory authorities.
- Information technology structure with web portal to support principal investigators (PIs) to make their therapeutic choice.
- Weekly clinical monitoring committee with investigators from multiple countries convening to present and discuss patients, and assist with decision-making, was immensely successful.
- Trial funded by a highly competitive peer-review European EU-FP7 grant of 3 million euros (funding only 2% of submitted grants) and also by philanthropy (2 million euros) and industry (1.5 million euros).

## 2.6. THE SPRING STRATEGY

The SPRING trial will build on the established infrastructure from the WINTHER trial. It will, however, be a strategic second-generation trial, incorporating the following additional approaches:

- Tri-therapy combinations instead of monotherapy will be tested
- Immunotherapy will be incorporated
- Genomics and transcriptomics will be integrated for correlation purposes at the end of the study
- The SIMS algorithm will be incorporated (1) for **correlation purposes at the end of the study.**

The simplified interventional mapping system (SIMS) algorithm will be applied to integrate genomic and transcriptomic data (1). SIMS merges knowledge about existent drugs and their impact on the hallmarks of cancer. Our integrative approach and new mathematical modeling converts thousands of genomic and other “omics” measurements into a simple result that enables selection of individualized rational therapies including combinations of targeted therapies (1).

More specifically, the use of SIMS can allow identification and scoring (from 1 to 10) of specific interventional points/nodes for drugs based on the pathways deregulated in each patient’s cancer. This approach for prioritizing intervention points for a patient is simple and easy to interpret.

The basic premise is that, when the genes associated with an intervention point are more disturbed (in terms of sequence and/or expression level), the intervention point is assigned a higher score and thus is more likely to be crucial to the tumor. From this, it follows that the more disturbed the genes of an intervention point are, the more likely it is that therapeutics targeting that point will benefit the patient. This new therapeutic approach of combination therapies aims to simultaneously block different biologic pathways and reduce the chance of developing secondary resistance. SIMS identifies within the hallmarks of cancer (11) only signaling and regulatory pathways that can be targeted with available therapeutic agents.

Our work suggests that using the SIMS algorithm to orient therapeutic decision would benefit from several major assets: The interrogation of dual biopsies of tumor/metastasis and its normal counterpart, combined with a comprehensive systems biology investigation and innovative bioinformatics and scoring systems, may enable matching each individual patient with the most appropriate treatment. One of the cornerstones of this new methodology is use of dual matched tumor tissue and normal tissue biopsies from the same patient, enabling the subtraction of transcriptomic background noise in each patient (9, 21).

We propose to test this novel SIMS algorithm **retrospectively** on the cohort of patients who will be treated with the tested tri-therapy. The concept of SIMS was published in a peer-reviewed journal (1 and appendix 1). SIMS enabled to estimate the frequency of occurrence of the activation of each target of the three drugs used in the combination.

## 2.7. CONSIDERATIONS CONCERNING THE BIOPSIES IN SPRING TRIAL

A cornerstone of the SPRING strategy is the interrogation of tumor tissue (from metastatic tissue or primary tumor) and matched normal tissue (namely bronchial mucosa) by bronchoscopy in order to investigate DNA and RNA and run the SIMS algorithm. In doing so, our utmost concern will be the safety of the procedures.

In a majority of cases, percutaneous core needle biopsy is a standard part of initial work-up. In order to perform standard molecular testing (EGFR, ALK) more than one biopsy (bronchoscopic and percutaneous) is often required in clinical practice and is supported by NCCN (Diag-A 1 of 2). A second biopsy at time of progression is also supported by NCCN in select cases for further molecular characterization (NSCL 16-17). Repeat biopsies for cancer progressing after initial treatment is a common practice.

In the SPRING trial, the additional biopsy of normal tissue is integral to the SIMS algorithm and the hypothesis is that it will improve precision oncologic therapy selection.

In our previous experience in the WINTHER study where 303 patients were registered, 246 underwent a dual biopsy of the tumor tissue and normal matched tissue of which 55 were dual biopsies in lung cancer patients. From the 55 lung cancer dual biopsied patients, 45 had CT-guided lung tumor core needle biopsies. 4 patients were observed in the hospital for 24 hours because they developed a small pneumothorax that resolved rapidly (among which 2 required chest tubes). There were no life-threatening complications.

Research biopsies are a frequent component of current clinical trials. In MD Anderson's experience in Oncologist 2011, a total of 281 research biopsies on 155 distinct patients and 42 lung biopsies had been done and 2 patients had a pneumothorax for rate of 4.8% (22).

Furthermore, a meta-analysis performed in April 2016 reported 8,133 CT-guided core needle biopsy procedures. The pooled rate of pneumothorax requiring intervention was 5.6% (23) (e.g., clinically relevant pneumothorax requiring placement of chest tube). The published complication rate of endobronchial forceps biopsy is 4% rate of minor bleeding with endobronchial forceps biopsy (24) and 1.5% rate of pneumothorax (25).

The following measures implemented in WINTHER will be applied to SPRING in order to mitigate any risk:

- Biopsy of lowest risk lesion performed by experienced interventional radiologist,
- As often as possible, biopsy of a liver lesion or lymph node (very low risk) to be chosen.

An Independent safety and data monitoring committee (DSMB) will review the overall patient safety during the trial.

In addition, the Informed Consent will be very detailed and clear about the risks of biopsy and the rationale for the dual biopsy approach. The interventional risk will be discussed with the patients in the context of the overall risk of their disease, the mortality risk of which is extremely high in lung cancer and will be juxtaposed to the potential benefits: Biopsies are a crucial component of the SIMS algorithm.

## 2.8. SUMMARY OF RATIONALE BACKGROUND AND STRATEGY

The standard of care in advanced disease—mainly cytotoxics or matched targeted monotherapies—has had modest impact on mortality as even responders inevitably develop resistance and succumb to their disease (7). Indeed, the fact that tumors are driven by multiple aberrant genes (9, 12, 13), and that resistance uniformly emerges in a Darwinian manner in patients treated with a single targeted therapy render the monotherapy paradigm unsuitable for most metastatic cancers.

With the aim of further enhancing clinical benefit and increasing survival, we propose to test a triple therapy combination of novel targeted drugs in NSCLC. This mirrors the approach that has been so successful in treating AIDS and select cancer types, such as certain leukemias and malignant lymphomas.

In the SPRING proof of concept trial, we selected three agents based on multiple criteria:

- To limit the toxicity profile of the combination, we selected a modulator of immune check point (anti PD-L1) in association with two small molecule tyrosine kinase inhibitors (TKI): anti CDK 4/6 (selective dual inhibitor of CDK 4/6) and an anti – VEGFR. The anti PD-L1 selected is avelumab, co-developed by MERCK and PFIZER. It demonstrated, so far, a good safety profile and is currently tested in various phase 3 programs (see Appendix 3).
- The selected TKIs, palbociclib and axitinib (PFIZER), are approved in other indications and have individually also a safe toxicity profile (see Appendix 3).
- Our data suggests a strong activation of these targets in a significant proportion of advanced NSCLC (see Appendix 4).

- We estimate that overall 85% of the patients treated in the trial will have a profile that is matched to at least one out of the three drugs: 10% matched with three drugs, 36% matched with two drugs and 39% matched with one drug.
- The three agents were made available for combination by PFIZER.
- Specific safety measures related to the administration of avelumab will be implemented in each participation center.

### 3. SPRING OBJECTIVES AND DESIGN

---

#### 3.1. PRIMARY OBJECTIVES

- To determine the safety of the tested 3-drug combination therapy based on NCI CTCAE v4.03; June 14, 2010.
- To assess activity parameters, including response rate (RR) by RECIST 1.1, duration of response, progression-free survival (PFS), overall survival (OS),
- To correlate clinical outcome with the predicted SIMS matching through a retrospective study.

#### Criteria of success:

- We will document best response in all patients. Patients shall be followed for at least six months on treatment (providing their tumors do not progress earlier) in order to document best response: The trial will be considered as meeting its primary endpoint if a 6-month response rate (% of patients achieving RECIST 1.1 complete or partial response within 6 months of treatment start) of 50% is achieved for patients who are fully matched according to the SIMS retrospective analysis and is superior to the partially matched arms. With a type I error of 10% and a power of 94%, 20 patients fully matched will be enough to demonstrate the usefulness of the approach assuming a null response rate of 20% based on the one-sided Fisher's exact test. This would require a cohort of 200 patients treated. Nevertheless, we intend to treat an initial cohort of 100 patients as an exploratory observational study. Pending clinical activity, the study could be extended to an additional 100 patients treated in order to attain sufficient statistical power to support the validity of the approach.
- SIMS will show clinical utility:
  - If the proportion of patients fully matched to the combination versus partially matched estimated using SIMS (20/80) is similar to the observed proportion in the SPRING cohort (maximum coefficient variability allowed 20%),
  - If fully matched patients show significantly better clinical outcomes than the partially matched ones and the fully or partially matched ones show significantly better clinical outcomes than the non-matched ones.

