Also we will compare the estimated numbers of patients in each of the arms as predicted by SIMS versus the observed distribution in the patients treated. Based on previous data published (1), the estimated match in PD-L1 positive (50 patients) is:

- Arm A: Fully matched group, with all three activated targets, will be seen in 10 patients.
- Arms B1 or B2: Partially matched group, with two activated targets (anti PD-L1 + CDK4/6 or anti PD-L1 + anti VEGFR), will be seen in 13 patients and 12 patients respectively.
- Arm B3: Remaining 15 patients will only be matched to anti PD-L1.

For the PD-L1 negative patients (50 Patients), they are further grouped into the following 4 subgroups:

- Arm C1: Partially matched group with two activated targets (CDK4/6 and VEGFR), will be seen in 11 patients.

- Arm C2 or C3: Partially matched group with one activated targets (VEGFR or CDK4/6), will be seen in 8 and 16 patients, respectively.
- Arm C4: Non-matched group, with none of the three activated target matched, will be seen in 15 of patients.

It is expected that half of the patients will be PD-L1 positive and half of the patients will be PD-L1 negative. The hypothesized 6-month response rate in Arm A (fully matched) is 50%; in Arms B1, B2, and C1 (partially matched with two targets) is 40%; in Arm B3 (matched with PD-L1 only) is 30%; in Arms C2 and C3 (partially matched with VEGFR or CDK4/6) is 20%; and in Arm C4 (non-matched group) is 10%. The expected 6-month response rate is 30% in the entire group assuming the triple therapy works.

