### 7.2.1. Statistical analysis of the primary efficacy end point

The primary efficacy evaluation for measuring a clinical meaningful improvement is defined as demonstrating an improvement of the primary efficacy endpoint of 6-month objective response rate from 20% (under the null hypothesis) to 50% (under the alternative hypothesis) in the fully matched arm. With 5% one-sided type I error, we need to treat 20 patients to demonstrate the usefulness of the tri-therapy approach to achieve and 86% power based on the exact binomial test. With an expected 10% of patients who will be fully matched, we need to enroll 200 patients in the study. All inevaluable patients will be replaced. **To ensure that patients will not receive ineffective treatments after sufficient evidence, two efficacy futility early stopping rules** will be implemented.

- The first futility early stopping rule will be applied after treating 14 patients with the tri-therapy at the RP2D level. If none of the 14 patients has 6-month response (CR or PR), the patient enrollment will be halted and the trial can be stopped for futility. This futility early stopping rule coincides with the first stage of the Gehan's design targeting 20% response rate with 95% confidence (26).
- The second futility early stopping rule will be evaluated every 10 patients after 20 patients are treated at the RP2D by applying the predictive probability (27). The trial can be stopped early if we see the following 6-month responses or less: 2 in 20, 3 in 30, 5 in 40, 6 in 50, 7 in 60, 9 in 70, 11 in 80, or 12 in 90 patients. The design has 5% type I error rate and 95% power with a null response rate of 10% and a target response rate of 30% at 6 months in the whole group. The probability of early stopping is 0.95, 0.31, and 0.04 if the response rate in the whole group is 10%, 20%, and 30%, respectively.

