- In addition to the futility analysis for early stopping of the trial if the triple therapy does not show minimum efficacy in the whole group, we will also look for efficacy signal in the subgroups. The triple therapy will be considered potentially effective if the posterior probability of response rate greater than 0.3 is larger than 60% in any of the predefined subgroups (Arm A, Arms B1-B3, Arms C1-C3, or any of the combined groups). Assuming a weak prior of Beta (0.1, 0.9), the treatment will be considered potentially efficacious if we see 4 responses in 10 patients, 7 responses in 20 patients, or 10 responses in 30 patients.
- In rare occasions that the early futility stopping criterion is met but the treatment shows potential efficacy in predefined subgroups, further discussions will be conducted among study PIs, sponsors, and regulatory agencies to determine whether study will be terminated or extended in specific subgroups.

These cohort size estimates are based on *in silico* data generated by SIMS using an independent set of data obtained from investigation of tumor and matched normal biopsies from the same patient. SIMS model will be considered clinically meaningful if the observed matches are similar to estimated matches, with a maximal tolerated coefficient of variability of 20%, and if fully matched group shows better outcome than partially matched groups.

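### The stated 94% and 86% power cover only fully matched patients against a fixed 20%, not the fully versus partially matched comparison that the success criteria also require

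*Combined protocol and SAP*

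**What the plan says.** **Section 3.1, Criteria of success, first bullet.** The primary endpoint is met if a 6-month response rate "of 50% is achieved for patients who are fully matched according to the SIMS retrospective analysis and is superior to the partially matched arms". The justification is: "With a type I error of 10% and a power of 94%, 20 patients fully matched will be enough to demonstrate the usefulness". It assumes a null rate of 20% and names a one-sided Fisher's exact test. The bullet adds that this needs 200 treated patients, that the first 100 are exploratory, and that the further 100 would supply sufficient power.

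**Section 3.1, second bullet (SIMS utility).** One condition is "If fully matched patients show significantly better clinical outcomes than the partially matched ones". Another compares the observed with the predicted proportion "fully matched to the combination versus partially matched estimated using SIMS (20/80").

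**Section 7.2.1.** The improvement sought is "from 20% (under the null hypothesis) to 50% (under the alternative hypothesis) in the fully matched arm". At a one-sided 5% error, 20 patients are needed "to achieve and 86% power based on the exact binomial test". There is no superiority clause in that rule. Later in the section, SIMS counts as clinically meaningful partly "if fully matched group shows better outcome than partially matched groups", with no mention of significance.

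**Section 1.4** repeats the 5% and 86% figures and says that 200 patients would give good power for the study. **Section 3.3.2** repeats the claim of sufficient power without a calculation.

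**Section 7** gives the expected arm sizes per 100 patients, starting with "Arm A: Fully matched group, with all three activated targets, will be seen in 10 patients", and the hypothesised response rate in each arm.

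No section gives a test, an alpha or a power for fully versus partially matched patients.

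**The concern.** The success rule has two parts and the power calculation addresses one of them. Because that calculation is labelled as a Fisher test and stands beside the superiority clause, a reader can easily take 94% as the power of a between-group comparison. The claim of sufficient power is also the reason given for adding a second 100 patients, so it bears on a sample-size decision.

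Testing Arm A against a fixed 20% cannot show that matching matters, since a regimen equally active in every arm could also pass. The comparison with partially matched patients is the part of the rule that speaks to matching, and its terms are left open. No test or alpha defines superiority, and it is not said whether 50% is a rate that must be observed or the hypothesised true rate. These choices could then be settled after the data are seen.

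**Working it through.** **1. Reproducing the plan's figures.** Inputs: n = 20, null 20%, alternative 50% (sections 3.1 and 7.2.1). With X binomial, the one-sample exact results are:

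| Success if | Size, P(X ≥ r given 0.20) | Power, P(X ≥ r given 0.50) | Matches |
|---|---|---|---|
| ≥ 7/20 | 0.087 | 0.942 | 94% at 10% (section 3.1) |
| ≥ 8/20 | 0.032 | 0.868 | 86% at 5% (sections 1.4, 7.2.1), within a point |

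Neither uses a comparator group. A true two-sample Fisher test of 50% in 20 patients against 20% in a comparator does not give 94% at 10%: it has 68% with 20 comparators and 89% with 150.

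**2. The partially matched group.** Section 7 defines it as Arms B1–B3 and C1–C3. Sizes per 100 are 13, 12, 15, 11, 8 and 16, total 75. B1, B2 and C1 (36 patients) are put at 40%, B3 (15) at 30%, and C2 and C3 (24) at 20%.

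Pooled rate = (36 × 0.40 + 15 × 0.30 + 24 × 0.20) / 75 = 23.7 / 75 = 31.6%.

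At 200 patients the comparison is 20 at 50% versus 150 at 31.6%.

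**3. Power of that comparison as a significance test.** Exact enumeration over all outcomes, 6-month response, one-sided:

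| Test | Alpha 5% | Alpha 10% |
|---|---|---|
| Fisher's exact | 39.6% | 53.4% |
| Pooled z | 49.7% | 63.3% |

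Mid-p and unpooled z fall between these. A result exactly on the assumptions (10/20 versus 47/150, since 150 × 0.316 = 47.4) gives a one-sided Fisher p of 0.08: significant at 10%, not at 5%.

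**4. The first rule of section 3.1, by reading, at its own 10%.**

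| Reading | Probability of passing |
|---|---|
| Reject 20% (≥ 7/20) and numerically higher than partially matched | 93% |
| Observed 50% (≥ 10/20) and numerically higher | 59% |
| Observed 50% and Fisher-significant | 50% |

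The 59% comes from the observed-50% requirement, P(X ≥ 10 given 0.50) = 0.588. Numerical superiority alone is met 94% of the time.

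**5. The 20/80 split.** In section 7 the whole cohort has 10 fully and 75 partially matched patients per 100. The PD-L1-positive half has 10 fully and 13 + 12 + 15 = 40 partially matched patients. 10 to 40 is 20/80, so the figure fits if it refers to that half, but section 3.1 does not say so. If the comparison were restricted in the same way (20 at 50% versus 80 at (25 × 0.40 + 15 × 0.30)/40 = 36.25%), Fisher power would be 23% at 5% and 34% at 10%.

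**The case against.** **Superiority may mean only numerically higher.** On that reading, combined with rejecting 20%, the rule passes 93% of the time, close to the quoted 94%. This stands for the first bullet. It does not reach the second bullet, which asks for a significant difference.

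**A reader might infer that the evaluation of SIMS is underpowered as a whole.** The documents do not support this. Section 1.2.2 states the hypothesis as a correlation of outcome with the number of activated targets, and section 3.1 also contrasts matched with non-matched patients. On section 7's figures at 200 patients, matched versus non-matched (170 at 33.8% versus 30 at 10%) has Fisher power of about 87% at 5% and 94% at 10%. A one-sided trend test over one to three targets has, by simulation, about 84% and 92%, although the plan names no such test. Fully versus partially matched is the weak contrast, but it is one that the plan itself makes a condition.

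**The utility clause speaks of clinical outcomes, not only response.** This is correct. The figures above are for 6-month response. Power for PFS or OS cannot be derived, because the documents give no such assumptions by match group.

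**The 5% figures borrow an alpha from another section.** This is fair: section 3.1 states 10%, so 53–63% is the range to set against its 94%. The 5% range matters only because sections 1.4 and 7.2.1 use 5%.

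**The study is exploratory.** The second 100 patients need an amendment, section 7.5 allows sample-size re-estimation, and section 7.6 says that findings need validation. This lowers the stakes, but it does not make the quoted power apply to the comparison.

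**Conclusion.** The point holds and should be fixed. The 94% and 86% are correct for 20 fully matched patients against a fixed 20%, and for nothing else in the success criteria. The Fisher label is an error. For 6-month response, fully versus partially matched has about 53–63% power at section 3.1's 10% and 40–50% at 5%, and the first success rule passes anywhere from about 50% to 93% of the time at 10%, depending on terms that the plan leaves undefined.

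The figures assume 200 treated patients with the second cohort run like the first (the first scenario in section 1.4), group sizes at their expected values, the partially matched arms pooled, and a SIMS score for every patient. Section 3.3.2 allows treatment after failed biopsies, so the last assumption is favourable. Selecting subgroups for the second cohort (the second scenario) would need a separate calculation.

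**What to change.** 1. In section 3.1, replace the Fisher label with a one-sample exact binomial test, and state that 94% and 86% apply only to Arm A against 20%.
2. Set one success rule and one alpha across sections 1.4, 3.1 and 7.2.1. Name the test for superiority, and say whether 50% is an observed threshold or the hypothesised rate.
3. State the resulting power for fully versus partially matched at 200 patients under the first scenario of section 1.4. Limit the wording on good or sufficient power in sections 1.4, 3.1 and 3.3.2 to the Arm A test.
4. If 20/80 refers to the PD-L1-positive patients, say so, since the whole-cohort split in section 7 is 10 to 75.

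The cost is protocol wording and one restated power calculation, with no added patients, data or procedures.
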